1 PROTOCOL SUMMARY

1.1 SYNOPSIS

Title: Phase I Study to Assess the Safety and Activity of Combination Therapy using a Novel Monoclonal Antibody, VRC07-523LS, and the Latency Reversal Agent, Vorinostat, to Reduce the Frequency of Latent, Resting CD4+ T Cell Infection in participants with HIV-1 infection suppressed on ART (The VOR-07 Study)

Study Description: Participants with HIV-1 Infection on ART with a CD4 T cell count ≥ 350 cells/mm³ and viral suppression for ≥ 24 months. Participants will receive two series of combination therapy consisting of one (1) intravenous (IV) dose of VRC-HIVMAB075-00-AB (VRC07-523LS) followed by 10 oral (PO) doses of Vorinostat (VOR) taken every 72 hours. Each series will last approximately 1 month and the two series will be separated by at least one month. Combination ART is (ART) maintained throughout the study.

Objectives:

Primary Objective:

1. To evaluate the safety and tolerability of combination therapy with VRC07-523LS and VOR in HIV-infected participants on ART.

Other Objectives:

1. Explore the effect of two cycles of VRC07-523LS and VOR on the frequency of latent, resting CD4+ T cell infection.
2. Explore the influence of VOR given with VRC07-523LS on low-level plasma viremia as measured by low level viremia assay in participants who maintain suppression on ART.
3. Compare HIV RNA expression within resting CD4+ T cells in HIV-infected participants on stable ART before and after combination therapy with VRC07-523LS and VOR measured at baseline (Step 1) and after the second series (Step 4).
4. Explore the impact of combined therapy with VRC07-523LS and VOR on the quantity of integrated proviral DNA quantification in T cell populations.
5. Characterize viral envelope sequences detected in plasma or cells that are not neutralized by VRC07-523LS from baseline to post-treatment with VRC07-523LS and VOR.
6. Evaluate the pharmacokinetics of VRC07-523LS combined with VOR and determine whether anti-drug antibody (ADA) to VRC07-523LS can be detected in recipients administered VRC07-523LS in combination with VOR.

Endpoints:

Primary Endpoint:

1. Safety: Occurrence of at least one \geq Grade 3 adverse event (AE) including signs/symptoms, lab toxicities, and/or clinical events that is possibly, probably, or definitely related to VOR or VRC07-523LS

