estimated to be 33 ± 10 days. The 28 day trough following one dose of VRC07-523LS 40 mg/kg IV was 272 (53 mcg/mL) (n=3) (IB, version 4.0, February 26, 2018).

Vorinostat (VOR)

VOR is a potent inhibitor of HDAC activity and binds directly to the catalytic pocket of HDAC enzymes. VOR, at low nanomolar concentrations, inhibits the enzymatic activity of HDAC1, HDAC2, and HDAC3 (Class I) and HDAC6 (Class II) (34-36). Concentrations of VOR that cause the accumulation of acetylated histones also induce cell cycle arrest, differentiation, or apoptosis of transformed cells (35). VOR induces apoptosis in a wide variety of transformed cells in culture, including cutaneous T-cell lymphoma (CTCL) cell lines, circulating atypical T-cells derived from patients with CTCL, human lymphoma cell lines and murine erythroleukemia (MEL) cells. VOR also inhibits proliferation of cultured transformed human cells derived from leukemias, non-small cell lung carcinomas, colon carcinomas, central nervous system tumors, melanomas, ovarian carcinomas, renal cell carcinomas, prostate and breast cancers. In cultured human transformed cell lines, VOR has synergistic or additive activity in combination with other cancer therapies, including radiation, kinase inhibitors, cytotoxic agents, and differentiating agents (34, 35, 37-44). In vivo, VOR demonstrates anti-neoplastic activity in a variety of rodent tumor models including xenograft models of human prostate, breast, and colon carcinoma. While it has been assumed that the effects of VOR on histone acetylation underpin its biological activities, a number of other proteins are regulated by histone acetyltransferases (HATs) and HDACs and may be targeted by VOR (45). Several non-histone proteins, (e.g., tubulin, Hsp90, and p53) are known to be reversibly acetylated on lysine residues and undergo hyperacetylation following exposure to VOR (46-48). Acetylation of these proteins may also contribute to the antitumor activity of VOR. Please refer to the VOR Clinical Investigator's Brochure (CIB), edition 8, 8/1/2013, for detailed information.

VOR and HIV

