Pharmacokinetic samples will be collected at 3 time points in the study. These will be processed and stored for testing as required.

VRC07-523LS PK samples

Pharmacokinetic samples will be collected at 3 time points: at baseline and after antibody administration at Days 29 (Visit 6) and 89 (Visit 11). These will be processed, stored, and shipped for testing as required.

Anti-Drug Antibody (ADA) Detection Assay

ADA will be measured by using the Meso Scale Discovery (MSD) platform with VRC07-523LS as the target antigen. Anti-VRC07-523LS antibody assays will be performed on serum samples collected at baseline and after antibody administration at Days 29 (Visit 6) and 89 (Visit 11). Serum will be stored at other visits per the SOE. Additional ADA testing may be performed on participants if indicated.

Virology and Viral Sequence Analysis

Samples will be collected per the SOE. Samples will be processed, stored, and analyzed as required.

Cell associated RNA Assay (caRNA)

Samples collected to isolate resting CD4 T cells and run the caRNA assay to have an additional baseline point. It will provide an idea of the baseline variation in caRNA of a given participant. This is important in trying to measure a change in caRNA after the intervention.

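### Routine ADA assays stop at Day 89, 29 days after infusion 2 and at a high drug level, while later and lower-drug serum is stored without scheduled testing

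*Combined protocol and SAP*

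**What the plan says.** Objective 6 in the Synopsis (section 1.1) is partly to "determine whether anti-drug antibody (ADA) to VRC07-523LS can be detected in recipients administered VRC07-523LS in combination with VOR". Section 3 lists the same aim as tertiary/exploratory. In both places the matching endpoint covers only pharmacokinetics or serum concentrations, and section 9.4 describes no ADA analysis. The ADA paragraph of section 8.1 is therefore the only text that fixes how the question will be answered:

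- **Assay:** "ADA will be measured by using the Meso Scale Discovery (MSD) platform with VRC07-523LS as the target antigen". No drug tolerance, sensitivity or cut point is stated.
- **Scheduled times:** "Anti-VRC07-523LS antibody assays will be performed on serum samples collected at baseline and after antibody administration at Days 29 (Visit 6", and then Day 89 (Visit 11).
- **Other samples:** "Serum will be stored at other visits per the SOE".
- **Exception:** "Additional ADA testing may be performed on participants if indicated". No trigger is defined.

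The ADA row of the Schedule of Events (section 1.3), as I read the table, marks samples at Day 0, Day 29, the Pre-Visit (Visit 7), Day 60, Day 67, Day 74, Day 89 and End of Study. Section 8.1 places the VRC07-523LS PK samples at the same three times as the scheduled ADA assays.

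**The concern.** Two features of the assayed times work against finding ADA.

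- **Delay.** After infusion 2 the only scheduled assay is at 29 days. The End of Study sample, drawn later, is not scheduled for assay.
- **Drug level.** The drug itself is the assay's target, so drug in the sample may compete for any ADA present. Both post-dose assays fall where circulating drug is high, and Day 89 also carries drug left over from infusion 1.

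A report that no ADA was detected would be read as the answer to objective 6, although the serum best placed to show late ADA had not been routinely examined. There is also no scheduled assay between Day 29 and infusion 2. ADA status at re-exposure would help to interpret a reaction to the second infusion, and section 2.3.1 itself lists ADA formation among the risks of antibody administration.

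**Working it through.** The documents give no detection rate or sample size for ADA, so there is no ADA figure to reproduce. The nearest n=12 figure is the exact one-sided 95% upper limit for 0 of 12 in section 9.2: 1 - 0.05^(1/12) = 0.221, which agrees with the stated 0.22.

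**Step 1: timing (no PK model needed).** Infusion 2 is on Day 60. Visit 12 is 5-8 weeks later (Days 95-116), and End of Study is 2-4 weeks after that (Days 109-144). End of Study is therefore 49-84 days after infusion 2 and 20-55 days after the last scheduled assay.

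**Step 2: drug levels.** Inputs from section 2.2: a 28-day trough of 272 mcg/mL after one 40 mg/kg dose (n=3) and 33 ± 10 days, read as the VRC07-523LS half-life (HL). That reading is an assumption, because the start of the sentence is not in the text available to me. I use HL = 33 days, with a range of 23-43. Each infusion contributes

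C(t) = 272 × 2^(-(t - 28)/HL), with t in days since that infusion,

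and the contributions are added. At HL = 33:

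- Day 29: 272 × 2^(-1/33) = 266
- Before infusion 2 (Day 60): 272 × 2^(-32/33) = 139
- Day 89: 272 × 2^(-61/33) + 272 × 2^(-1/33) = 75.5 + 266 = 342
- End of Study, Day 109: 272 × 2^(-81/33) + 272 × 2^(-21/33) = 225
- End of Study, Day 144: 272 × 2^(-116/33) + 272 × 2^(-56/33) = 108

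| Sample | Scheduled for assay? | mcg/mL, HL 33 | HL 23 to 43 |
|---|---|---|---|
| Day 29 | yes | 266 | 264-268 |
| Before infusion 2 | no | 139 | 104-162 |
| Day 89 | yes | 342 | 307-369 |
| End of Study, Day 109 | no | 225 | 168-268 |
| End of Study, Day 144 | no | 108 | 59-152 |

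**Step 3: contrast.** Pre-infusion-2 serum holds 139/266 = 0.52 of the Day 29 level (0.39-0.61 over the half-life range). End of Study holds 225/342 = 0.66 down to 108/342 = 0.31 of the Day 89 level (0.19-0.72). Against Day 29, End of Study is 0.84 down to 0.40 (0.22-1.00), so an early End of Study sample at a 43-day half-life has the same drug level as Day 29.

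**Step 4: what masking could do (illustration with assumed sensitivities).** If 0 of 12 are positive and the assay detects a fraction s of true ADA cases, the upper limit on the true rate is 0.221/s: 22% at s = 1.0, 28% at 0.8, 37% at 0.6 and 55% at 0.4. The documents do not say which s applies.

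**Limits of the model.** The trough rests on three people; changing it scales every level alike and leaves the ratios unchanged. For VRC01, section 2.2 reports 28-day troughs rising from 57 to 89 mcg/mL at 40 mg/kg, a ratio of 1.56. The same one-phase method with a 15-day half-life and an assumed 28-day interval gives 1 + 2^(-28/15) = 1.27. Levels after infusion 2 may therefore be higher than shown.

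**The case against.** The strongest reply has five parts.

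1. **Bias is not shown.** A reader might infer that the ADA objective is biased toward a negative answer. That needs drug interference at about 266-342 mcg/mL, and the documents give no drug tolerance, assay format or sample pre-treatment. This stands: masking is a risk of unquantified size.
2. **The stored sera are not excluded from testing.** A reader might infer that they will never be assayed, but section 8.1 allows extra testing if indicated, and a second-infusion reaction is an obvious occasion. This stands in part. Testing prompted by events can help explain an individual reaction, but with no trigger defined and testing of selected people only, it cannot say whether ADA occurs across all participants.
3. **The stored sera also hold drug.** They hold about 59-268 mcg/mL over the half-life range. Testing them may reduce interference but would not remove it, so the documents give no ground for treating End of Study as the definitive result. This stands.
4. **Days 29 and 89 have a purpose.** PK samples are scheduled at those times, so a negative can be read beside a drug level, whereas section 8.1 places no PK sample before infusion 2 or at End of Study. This stands, and the fix allows for it. But knowing the drug level does not recover ADA that appears later.
5. **Timing is less one-sided than it looks.** Day 89 is 89 days after first exposure, and pre-infusion-2 serum is earlier than Day 89; only End of Study is later than every scheduled assay. This stands. ADA is also exploratory, and section 2.3.1 reports that none had been observed with VRC01-class antibodies.

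**Conclusion.** The point holds as a gap in routine coverage. No scheduled assay falls more than 29 days after infusion 2, although serum at 49-84 days is already collected, so ADA first appearing after Day 89 would not be routinely detected. This part rests on the visit schedule alone.

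The drug-level part is weaker. The assayed samples hold about 1.9 times (Day 29 against pre-infusion 2) and 1.5 to 3.2 times (Day 89 against End of Study) the drug in the stored ones at a 33-day half-life. That gives a plausible risk of false negatives but no measure of it. It assumes one-phase decay, a trough from three people, the half-life reading described above, and an assay open to drug interference.

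No primary conclusion depends on ADA. This is a cheap improvement of low to moderate priority.

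**What to change.** In the ADA paragraph of section 8.1:

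- Schedule ADA assay of the stored pre-infusion-2 serum (Visit 7, or Day 60 if drawn before the infusion) and of the End of Study serum for every participant, alongside baseline, Day 29 and Day 89.
- Report ADA at any post-dose time, with results by visit. Do not label End of Study the definitive value.
- State the assay's drug tolerance and interpret each negative against it and the VRC07-523LS level. As no PK sample is scheduled at the added visits, measure drug in the same stored serum where volume allows.

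Cost: 2 × 12 = 24 further ADA assays, plus the optional drug-level measurements, on serum the schedule already collects. No extra visit or blood draw is needed. The visit marks in the ADA row should be confirmed against the source Schedule of Events before the text is changed.

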8.2 SAFETY AND OTHER ASSESSMENTS

All clinical and laboratory information required by this protocol is to be present in the source documents. Reference the Source Document Guidelines on the DAIDS web site for information about what must be included in the source document.

<http://www.niaid.nih.gov/labsandresources/resources/daidsclinrsrch/documents/sourcedocappndx.pdf>

All stated evaluations are to be recorded unless otherwise specified. This includes events that meet the International Conference on Harmonisation (ICH) definitions for a serious adverse event.

- Results in death
- Life-threatening
- Requires inpatient hospitalization or prolongation of existing hospitalization
- Results in persistent or significant disability/incapacity
- Congenital anomaly/birth defect
- Other important medical event that may not be immediately life-threatening or result in death or hospitalization but may jeopardize the participant or may require intervention to prevent one of the other outcomes listed in the definition above.

To grade diagnosis, signs and symptoms, and laboratory results, reference the DAIDS Table for Grading the Severity of Adult and Pediatric Adverse Events (DAIDS AE Grading Table), corrected Version 2.1, July 2017, on the DAIDS RSC website at <http://rsc.tech-res.com/clinical-research-sites/safety-reporting/daids-grading-tables>

Medical History and Medical History Updates

The medical history must include all signs and symptoms and all diagnoses regardless of grade within the past 30 days prior to entry.

Document:

- all allergies to any medications and their formulations
- date of birth, gender at birth, race and ethnicity of participant
- nadir CD4 and pre-ART HIV-1 RNA level, if available (if nadir documentation is not available, then collect and record participant recall)

The medical history evaluation will be assessed and recorded at the screening visit. Updates to medical history will occur at all clinical study visits. Any reported sign, symptom, and/or new diagnoses occurring after the participant signs the study consent but prior to the administration of the first dose of study product will be recorded in the medical history (pre-existing condition) unless the reported event is related to a protocol procedure.

Clinical Laboratory Testing for Safety

Hematology

Hemoglobin, hematocrit, white blood cell count (WBC), differential WBC, absolute neutrophil count (ANC), and platelet count will be performed in real time at the local laboratory.

STAT CBC with differential is required prior to each leukapheresis procedure done at UNC unless completed within 24 hours of the procedure and the results of that test are available to the Apheresis Lab. Apheresis collections completed at the American Red Cross require a CBC within the 30 days prior to the procedure.

Liver Function Tests

Total bilirubin, AST (SGOT), ALT (SGPT), and alkaline phosphatase will be performed in real time at the local laboratory.

NOTE: For participants on ritonavir boosted atazanavir, total and direct bilirubin should be measured.

Blood Chemistries

Screening lab evaluation are done fasting and includes electrolytes (sodium, chloride, potassium, CO₂/bicarbonate), glucose, blood urea nitrogen (BUN), creatinine, calcium, albumin, magnesium, lipase, and total protein in real time at the local laboratory.

Safety lab evaluations throughout the study include electrolytes (sodium, potassium, chloride, CO₂/bicarbonate), BUN, creatinine, calcium, magnesium, and glucose (also reference Pre-Infusion Safety Lab Assessment).

Creatinine and Creatinine Clearance

Creatinine clearance (eGFR) calculations will use the CKD-EPI equation. This calculation can be found at https://www.qxmd.com/calculate/calculator_251/egfr-using-ckd-epi

The creatinine clearance (eGFR) will be required for study enrollment eligibility. The study assesses serum creatinine level at all of the safety lab checks and uses the serum creatinine value for toxicity grading.

The creatinine clearance (eGFR) value reported as part of the lab report of serum creatinine level will be re-assessed and re-calculated if incidental finding indicates a value \geq Grade 3. The re-calculated value using the CKD-EPI equation will be used to determine the severity of the lab abnormality.

Pre-Study Treatment Safety Lab Assessments

Participants will have a Pre-Study Treatment Safety Lab Assessment prior to receipt of VRC07-523LS infusions at Day 0 and Day 60. The safety lab results obtained in this assessment must be within the eligibility criteria parameters established for this study. Labs that fall outside the parameters can be repeated one time only to qualify the participant to proceed on study.

After repeat testing, any lab value that remains outside the guidelines but considered clinically non-significant and documented as such by the study clinical PI (or designee), must be reviewed and approved by the protocol team and/or safety committee prior to the infusion.

Time points for the Pre-Study Treatment Safety Lab Assessment are:

- Step 2, Day 0 – prior to the administration of the first infusion. These labs can be performed up to 7 days prior to the infusion.
- Step 3, Visit 7, Pre-Visit – prior to the administration of the 2nd VRC07-523LS infusion

Follicle Stimulating Hormone (FSH) Test

This test is done at screening to document menopause in women who have been without a period for > 12 months.

Serum Pregnancy Test

A negative serum pregnancy test (to rule out pregnancy) is required on all women at screening.

A negative serum pregnancy test is required at each visit prior to VRC07-523LS infusion, and within 72 hours of the first VOR dose in Step 2 and Step 3 regardless of documented procedures that prohibit pregnancy.

In addition, a serum pregnancy test should be performed at any time if pregnancy is suspected. Because the study has no direct clinical benefit, this added protection is warranted.

Hepatitis Screen

Both hepatitis tests (HCV AB and HBsAg) must be negative or non-detected to be included on the study. A positive HCV AB test reflexed to Hepatitis C RNA revealing a negative result is acceptable.

Eligibility will be determined based on negative testing, per above definition at screening and prior to the Day 60 visit.

RPR

This test is done to rule out clinically active untreated syphilis at screening.

Participant may participate on study following documentation of adequate treatment of syphilis at screening (Visit 1). Participants diagnosed with syphilis while on study, will be referred for and require documentation of treatment prior to the 2nd infusion at Day 60. These infusions can be delayed until a minimum of 14 days post treatment for syphilis per recommendation by the study PI (or designee).

Fasting Lipid Panel

Total cholesterol, HDL, LDL calculation, VLDL calculations and triglycerides are obtained at screening.

Prothrombin Time (PT), INR, and APTT

Evaluated at the Screening Visit.

CD4⁺/CD8⁺

All study required absolute CD4⁺/CD8⁺ count and percentages must be obtained from a laboratory that possesses a CLIA certification or equivalent.

Eligibility will be determined based on a CD4⁺ cell count \geq 350 at screening and at Visit 7 (within 7 days prior to Day 60 Visit).

Plasma HIV-1 RNA

All study-required HIV-1 RNA must be performed by a laboratory that possesses a CLIA certification or equivalent.

Eligibility will be determined based on an HIV-1 RNA value <50 copies/mL at screening and at Visit 7 (within 7 days prior to Day 60 Visit).

Urinalysis

A full urinalysis with microscopic evaluation will be performed at screening.

Dipstick testing (including protein, glucose, hemoglobin, pH, and ketone) will be done at select visits. After screening, microscopic analysis will only be done in the event of abnormal results from dipstick testing.

Clinical Procedures for Safety

VRC07-523LS Administration

Record the infusion, including dose, and time of the study treatment administration. Record where the IV was inserted (location). If entire dose is not administered for any reason, notify the study PI and document the reason.

The following will be completed at each infusion administration visit:

- Confirm participant name and DOB with study treatment label, research chart, and verbal confirmation of same from participant with a second licensed provider.
- Participant must be seated in a secure chair or lying in a bed for the infusion.
- Document time of administration.
- Have emergency kit at bedside.

Post-Infusion Management

Observe participant and infusion site for a minimum of 60 minutes following the first infusion and a minimum of 30 - 60 minutes following the second infusion.

- Assess for site for a reaction every 15 minutes X 4, document observed reactions for 60 minutes following the first infusion and for every 15 minutes X 2 (at minimum) following the second infusion.
- Assess participant for local and systemic reactions every 15 minutes x 4, document observed reactions for 60 minutes following the first infusion and for every 15 minutes X 2 (at minimum) following the second infusion.
- Observe and assist participant when coming to a standing position for the first time following each infusion
- Obtain vital signs (BP, P, RR, and T) every 15 minutes for 60 minutes following the first infusion and every 15 minute for at least 30 minutes – 60 minutes following the second infusion. Document VS prior to discharge home.

Instruct participant to contact the study coordinator immediately with any concerns after leaving the clinic.

Provide participant post-infusion symptom log and instructions for completion prior to leaving the clinic. Post-infusion assessment includes the following:

- Contact participant between Days 4 and 6 post-infusion in the manner pre-determined by study coordinator and participant
- Review the symptom log at Days 4-6 with participant
- Collect and reconcile the symptom log with the participant at the Day 7 visit following each infusion

Solicited AE Assessments

Participants will be given a “Post-infusion AE Assessment” tool to use as a memory aid for tracking AEs that occur during the 3 days following the infusion. Participants will record daily temperature and symptoms.

For this study, solicited AEs occurring during the 3 days after receipt of study agent will include:

Localized Symptoms	Systemic Symptoms
• Erythema (redness)	• Fatigue
• Local pain/tenderness	• Headache
• Warmth at infusion site	• Fever >37.7°C or 99.9°F
• Induration (hardening or formation of a crust or scab)	• Chills
• Itching (generalized and local)	• Rashes
• Swelling	• Myalgia
• Skin discoloration	• Arthralgia
• Skin damage (vesiculation or ulceration)	• Nausea
• Vomiting	• Malaise
• Urticaria	• Non-exertional dyspnea
• Facial flushing	• Non-exertional tachycardia
• Unexplained diaphoresis	

Participants will also record the highest measured temperature daily. Participants should be instructed to take their temperature at least once daily, starting with the day of infusion (day 0), after leaving the clinic and through day 3 post-infusion.

Temperature should be taken orally or via infrared thermometry and in the evening whenever possible. If more than one measurement is made in a day (for example, due to feeling unwell), then the highest temperature taken that day should be recorded.

Participants will have a telephone interview with a study coordinator 4 -6 days following each VRC07-523LS infusion to review the solicited AE assessment tool. Any incidents or events identified that could be related to the infusion and are still unresolved after Day 3, will require participants to come into clinic for clinical assessment. Telephone conversation will be documented and signed off by the study PI.

Events occurring during the Solicited AE Assessment period that may require a clinic visit based on the judgment of a study clinician include:

- Rash,
- Urticaria,
- Fever of 38.6°C (Grade 2) or higher lasting greater than 24 hours,
- A significant impairment in the activities of daily living (such as those consistent with Grade 2 or higher impairment),
- Arthralgia or other clinical concerns

The study coordinator reviews symptom logs for accuracy and completeness and will collect log at the Day 7 and Day 67 visits. Additionally, participants will undergo clinical laboratory assays and clinical

evaluations to assess safety at every visit. Participants will also be asked to contact the study coordinator, or study PI or designee should they experience any adverse events at any time points during the study.

Reactogenicity Assessment

The participant will assess for reactogenicity (expected) symptoms from days 0 to 3 following each infusion on their post-infusion symptom card.

The daily maximum severity reached for each symptom during the 3-day assessment period will be reported. Study staff will follow new or unresolved reactogenicity symptoms to resolution. In general, participants self-reporting any post-infusion reaction greater than mild are to be evaluated by Study PI (or designee) within 48 hours after onset, unless the reaction is improving and/or has completely resolved. Institute appropriate countermeasures, including medical intervention or procedures, if clinically indicated.

Estimated Blood Volumes Associated with the Study Visits

Visit or Week #	Blood Volume (mL)	Visit or Week #	Blood Volume (mL)
Visit 1	50	Visit 8 Day 60	116
Visit 2	153	Visit 9 Day 67	18
Visit 3 Day 0	61	Visit 10 Day 74	18
Visit 4 Day 7	15	Visit 11 Day 89	173
Visit 5 Day 14	16	Visit 12	50
Visit 6 Day 29	158	Visit 13	135
Visit 7	70		

Cancer Registry

All participants who receive greater than 8 doses of VOR in a study are asked to enter a study cancer registry. The registry is maintained by the clinical program director of the UNC HIV Cure Center. Participants willing to participate in the registry are contacted annually for 5 years following the completion of their VOR dosing regimen. The UNC Cancer Registry is searched annually for new cancer diagnoses registered to any of the VOR recipients. Data on participants included in this registry will be provided in the Annual Reports to the FDA for this study.

